2.1.2 Sample Size Justification

This trial will enroll 120 subjects randomized in a 1:1 ratio to either Reltecimod 0.5 mg/kg (n=60) or placebo (n=60), both in addition to standard of care (SoC). Sample size analysis was performed assuming all patients will be evaluable for the primary endpoint due to using last observation carried forward (LOCF) for patients missing the creatinine value on Day 28. The primary efficacy hypothesis will be tested using an unadjusted χ^2 statistic with a one-sided $\alpha=0.05$ significance level. Rejection of the null hypothesis will only occur if investigational drug superiority is demonstrated. Statistical power was computed for a range of expected treatment group differences supported by the results of preliminary studies. The following table summarizes the statistical power for a total sample size of N=120 (60 per group) for various assumptions regarding the success rate in the investigational arm and assuming a success probability of 0.50 among controls. This sample size results in 89% power if the true success rates are 75% and 50% for the investigational drug and placebo, respectively, for a group difference of 25%. Power remains above 80% if the true group difference is at least 22% (Table 1).

Table 1. Computed Power			
Index	Control	AB103	Power
1	0.5	0.65	0.507
2	0.5	0.70	0.727
3	0.5	0.71	0.766
4	0.5	0.72	0.802
5	0.5	0.73	0.834
6	0.5	0.74	0.864
7	0.5	0.75	0.890

2.2 Randomization

120 patients will be recruited into the study and randomized to either 0.5 mg/kg Reltecimod or placebo in a 1:1 ratio. Randomization will be performed within site and according to the following stratification factors:

- **Acuity of AKI:** reflects whether or not AKI is diagnosed at time of presentation of abdominal infection or during the 48 hours following the suspected diagnosis of abdominal infection.
- **Subject Age:** ≥ 18 to ≤ 75 and > 75 to ≤ 85 years old
- Four computer-generated, blocked randomization lists will be provided for each site, one for each of the four strata defined on the basis of the 2 by 2 cross-tabulation of the two stratification variables. Within each block, half of the assignments will be to active drug and half to placebo, in random order. Block sizes will be varied.

The following provide details regarding randomization.

Biomedical Statistical Consulting will utilize software written in R Software (acceptable R versions > 3.1) to create the randomization schedule. The randomization inputs to this validated software are provided in Exhibit 1, with the exception of the final random seed utilized to generate the blinded randomization schedule. A draft randomization schedule will be generated with clearly marked “dummy” randomization treatment assignment (e.g., ‘DUMMY-Placebo’ and ‘DUMMY-Active’), and then exported to the necessary format for upload into the online randomization and study management system (RAVE Balance RTSM by Medidata Solution) administered by the Sponsor’s CRO (PharPoint Research, Inc.). The accurate upload of this “dummy” randomization schedule will then be verified by the unblinded study statistician, following the schedule provided by PharPoint Research, Inc. After verification, the process is repeated by the unblinded study statistician by rerunning the randomization software with updated seeds to determine the final (blinded) randomization schedule, with any “dummy-specific” notation removed. This final (blinded) randomization schedule is then uploaded to the online study management system utilizing the

identical process verified through the “dummy” randomization schedule. A variable indicating the blinded treatment allocations will not be part of the clinical study data to be managed by the data management CRO to avoid risk of unblinding through inadvertent data transfer. Therefore, only blinded study data will be available to the blinded primary study statistician and blinded analysis staff. The randomization schedule parameters were set so that there would be an excess number of potential sites to over at least 60 sites in the US and at least 50 sites in France, Belgium and Netherlands. For every potential site, the maximum number of possible subjects was 30. Block sizes were randomly set to 2 or 4. Within each block, an equal number of allocations were made to the active and placebo groups. Separate randomization schedules were provided for each of 4 strata defined on the baseline of the acuity of AKI diagnosis and age category as described above.

2.4 Control of Blinding and iDMC

An independent data monitoring committee (iDMC) will be established to evaluate the safety of the study. A detailed iDMC charter will be provided to clarify all relevant issues relating to firewalls to protect against potential operational biases. The charter will provide decision rules, composition of the iDMC members, and their conflict of interest statements.

The iDMC reviews of the safety data are is planned for after 60 patients (and possibly a second review depending on sample size re-estimation) have completed 28 days of the study.

For each planned iDMC review, all safety data on all patients who received one dose of study drug will be made available to the committee. The data reviewed by the iDMC will be unblinded and presented by treatment group to facilitate recommendations to the Sponsor. Data submitted to iDMC review will be unaudited.

A designated unblinded statistician will provide unblinded safety data to the iDMC using programs constructed and validated by the blinded Study Statistician and Statistical Programming Team.

The iDMC may also meet on an ad-hoc basis when immediate safety concerns arise. Thus, in case of urgency, the chair of the committee could address any questions or concerns regarding the safety of the patients.

As noted above, this study will remain blinded as to treatment allocation. The actual randomized treatment allocations will be kept by an unblinded statistician responsible only for managing the randomization process. The data variable indicating the blinded treatment allocations will not be part of the clinical study data to be managed by the data management CRO. Therefore, only blinded study data will be available to the primary study statistician and responsible primary programming staff.

There are three statisticians in this study with different roles:

- Unblinded study statistician - performs randomization and provides backup
- Unblinded iDMC statistician - independent statistician supporting iDMC operations
- Blinded primary study statistician – primary lead statistician

The role of the unblinded study statistician is:

- Perform final randomization
- Provide the randomization to the pharmacy vendor
- Provide randomized allocations in electronic form to the unblinded iDMC statistician
- Serve as a backup unblinded statistician

A second, unblinded statistician will work with the iDMC to provide unblinded data as necessary for iDMC deliberations. This second, unblinded statistician is from ACI, the CRO responsible for supporting the iDMC.

Analysis staff under the direction of the primary lead statistician, will develop SAS based programs to process clinical data provided by the blinded data management CRO and to populate all planned safety analysis tables and listings. This development phase includes using a pseudo randomization

for purposes of table generation. The programming and relevant data will be provided to the independent unblinded iDMC statistician.

3 Description of variables to be included in statistical analyses

3.1 Medical and Surgical History

A complete medical history identifying both clinically relevant past medical and surgical conditions as well as active medical or surgical conditions will be reported on the Medical History eCRF. All chronic medications will be identified and characterized by trade or generic name, route of administration, as well as reason for use.

Baseline signs and symptoms, or adverse events occurring between signing the informed consent to receiving study drug, should be captured on the Baseline Signs and Symptoms eCRF.

3.2 Physical Examinations

Physical examinations will include a clinically appropriate examination of vital organ systems. These should include at a minimum the cardiovascular, respiratory, abdomen, extremities, and neurologic body systems.

3.3 Interim Physical Examinations (Symptom-Driven)

Interim PE will be targeted to include clinically appropriate examination of specific organ systems based on patient related signs and symptoms.

3.4 Concomitant Medication

All concomitant medications, including ancillary, antimicrobials, immunosuppressant, and nephrotoxic drugs (with the exception of over the counter medications (unless an antimicrobial, immunosuppressant or nephrotoxic drug), vitamins, laxatives, intravenous fluid and electrolyte replacement, parenteral nutrition, topical medications (unless an antimicrobial) and other selected medications as described in the Study Procedure Manual), will be entered into the eCRF and identified by their generic or trade name. Information about antimicrobial medications immunosuppressants, and nephrotoxic drugs should include the dose, dosing frequency, route of administration, duration (start and stop times and dates), and reason for administration (to treat primary or secondary infection or for surgical prophylaxis). Information to be collected about non-antimicrobial medications should include generic or trade name, route of administration, duration (start and stop dates) and reason for administration.

Timing and adequacy of antibiotic therapy (based on institutional guidelines, baseline pathogens and antimicrobial sensitivity) will be reviewed by the Principal Investigator.

3.5 Abdominal Infection and NSTI Type

The type of intra-abdominal process (e.g. complicated appendicitis or diverticulitis, peritonitis due to perforation of the stomach or small or large intestine, gangrenous or necrotic infected bowel or organ; or post-traumatic peritonitis) causing peritonitis and abdominal sepsis will be captured along with the type of surgical or interventional procedure to establish source control. NSTI type will be categorized as Necrotizing Fasciitis, Fournier Gangrene, Gas Gangrene and Other.

3.6 Vital Signs

Vital signs include heart rate, systolic and diastolic blood pressure, respiratory rate (spontaneous, assisted or controlled) and temperature. While these data points may be determined many times during the course of the patient's hospitalization, recording vital signs (first set of vitals on that day) in the eCRF will be based on once daily readings for specified time sequences according to time and events (see Appendix A, Section 18.1 of the Clinical Study Protocol).

3.7 Clinical Scores

Clinical scores/criteria components will be collected in the study. APACHE II score criteria will only be collected at screening (see Section 18.2 of the Clinical Study Protocol) while SOFA score will be collected throughout the study (see Section 18.3 of the Clinical Study Protocol). APACHE II will be used to determine disease severity while SOFA score will be evaluated as a secondary clinical endpoint. Individual parameters of the SOFA score will be collected and be correlated to response. All scores will be calculated retrospectively. Data will be recorded in the eCRF at specified time points according to time and events (see Section 18.1 of the Clinical Study Protocol).

3.7.1 SOFA Score Definition

Screening SOFA score: includes measurements of six organ systems (cardiovascular, respiratory, renal, coagulation, GI/hepatic, and CNS) with data values evaluated any time after arrival at study site hospital. *Follow-up SOFA scores:* measurements of (the same) six organ systems with data values measured on Days 1, 3, 7, and 14, and calculated retrospectively.

Where it is not possible to take arterial blood gases to determine the SOFA respiratory parameter, SpO₂ value can be converted to a PaO₂ value to allow calculation of the PaO₂/FiO₂ ratio.

For this study, the liver component is excluded in the primary total sum score, and the resulting sum score is referred to in this study as 'mSOFA'.

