6.1 Inclusion Criteria

1. Age: 18 up to and including 85 years.
2. Has either suspected or confirmed diagnosis of abdominal infection with planned or completed surgical (laparotomy or laparoscopy) or interventional radiologic procedures within 24 hours of evaluation by medical personnel, or surgically confirmed NSTI, requiring treatment with parenteral antibiotics. Recommended surgical or interventional radiologic procedures for abdominal infection be performed with 12 hours of evaluation by medical personnel.

A. Abdominal Infection

- a. Suspected clinical diagnosis of abdominal infection as evaluated by the attending surgeon including any of the following clinical criteria
 - Abdominal pain and/or tenderness
 - Localized or diffuse abdominal wall rigidity
 - Mass
 - Ileus

AND

- Any of the following radiologic findings
 - Free air (Plain film, CT or MRI scans)
 - Intraabdominal abscess (ultrasound, CT or MRI scans)
 - Free peritoneal fluid (ultrasound, CT or MRI scans)

OR

- b. Confirmed diagnosis of abdominal infection by any of the of the following criteria
 - Perforation and/or necrotic bowel with surgical confirmation of peritonitis
 - Presence of intraabdominal abscess by surgical confirmation or

drainage of purulent fluid from interventional radiologic procedure

OR

B. Necrotizing Soft Tissue Infection

- Surgical confirmation of NSTI by attending surgeon (e.g., presence of necrotic tissue, thrombosed vessels in the subcutaneous tissue, lack of bleeding and “dishwater” (cloudy, thin, gray) fluid due to presumed bacterial infection (necrotizing cellulitis (most commonly group A strep), necrotizing fasciitis, necrotizing myositis and myonecrosis, NSTI of the perineum, bacterial synergistic gangrene, Clostridial gas gangrene) that may be supported by specific signs and symptoms (e.g., tense edema outside area of compromised skin, pain disproportionate to appearance, skin discoloration, ecchymosis, blisters/bullae, necrosis, crepitus, and or subcutaneous gas).
3. SOFA score ≥ 2 (in any one or combination of the 6 major components of the SOFA score), measured as close as possible to study drug administration (but before study drug is administered).
 4. Planned or current admission to an ICU or step down unit (or equivalent).

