- Collect data on additional amputations if NSTI
- Collect data on acute RRT
- Record additional relevant procedures related to the kidney (e.g., renal biopsy)
- Record any imaging that evaluates the kidney
- Record any follow-up surgical or interventional radiologic procedures for previously documented abdominal infection or NSTI
- Symptom-driven interim PE
- Vital signs (to be taken during the morning tests)
- Critical care parameters (dates and times of assisted ventilation, vasopressor use, ICU /hospital stay)
- Record any hospital re-admissions (if previously discharged for original sepsis-related hospitalization)
- Serum creatinine
- Assess lesion status if NSTI (healing/progression/significant change in appearance) if accessible for visible assessment at time of debridement or routine dressing change
- Record Survival

Visit 7 (Day 14 [±1 day])

- Weight
- Collection of AEs/SAEs, including secondary infections
- Collect data on acute RRT
- Record additional relevant procedures related to the kidney (e.g., renal biopsy)
- Record any imaging that evaluates the kidney
- Record any follow-up surgical or interventional radiologic procedures for previously documented abdominal infection or NSTI
- Concomitant medications

- Safety laboratory tests (Chemistry, Hematology)
 - Full chemistry panel (see Section 9.2.11)
 - CBC with differential and platelet count
- Spot urine for albumin to creatinine ratio
- PE (visiting nursing service does not perform if outpatient)
- Vital signs (to be taken during the morning tests if still hospitalized)
- Standard CRP
- Collect blood for serum for storage (immunogenicity testing)
- Critical care parameters (dates and times of assisted ventilation, vasopressor use, ICU /hospital stay)
- Record any hospital re-admissions (if previously discharged for original sepsis-related hospitalization)
- Systemic response: collect data for SOFA parameters
 - All efforts should be made to obtain the actual measurements of SOFA parameters at these visits-may use SpO₂ value (and record FiO₂) if arterial blood gas is not clinically indicated.
 - Platelet count, creatinine and total bilirubin values required for SOFA components can be obtained from safety laboratories performed at this visit.
 - In case a patient is discharged from hospital prior to these days SOFA parameters should be obtained on the same day of discharge.

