9.2.10.1 SOFA Score Definition

Screening SOFA

Includes measurements of 6 organ systems (cardiovascular, respiratory, renal, coagulation, GI/hepatic, CNS). Screening SOFA score should be evaluated any time after arrival at study site hospital and within 6 hours prior to study drug administration.

SOFA Score

Measurements of 6 organ systems, including CNS. To be measured on Days 1, 3, 7, and 14, and calculated retrospectively.

SOFA Respiratory Parameter

In case it is not possible to take arterial blood gases to determine the SOFA respiratory parameter, SpO₂/FiO₂ ratio can be imputed for PaO₂/FiO₂ ratio.

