10.2 Secondary Efficacy Measures

- Rates of the primary endpoint at Day 14 between the Reltecimod- and placebo-treated patients
- To compare time to the primary endpoint between the Reltecimod- and placebo-treated patients
- AKI-free days over 14 and 28 days
- Resolution of organ dysfunction (organ resolution is defined as having a total SOFA score of ≤1) at Day 14
- Resolution of specific organ dysfunction defined as having an individual organ SOFA score of ≤1 at Day 14
- Critical care and hospital stay parameters
 - Hospital length of stay

- ICU-free days in 28 days
- Ventilator days
- Ventilator free days in 28 days
- Vasopressor days
- Vasopressor free days in 28 days
- RRT free days (days alive and free of RRT) in 28 days
- Patient survival at Days 14 and 28
- Presence of Stages 1, 2 or 3 AKI (using the KDIGO criteria) in patients with abdominal sepsis or NSTI

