12.2 Secondary Effectiveness Endpoints

The secondary effectiveness endpoints for this study:

- Rates of the primary endpoint at Day 14 between the Reltecimod- and placebo-treated patients.
- To compare time to the primary endpoint between the Reltecimod- and placebo-treated patients over 14 days
- AKI-free days over 28 days
- Time to the primary endpoint
- Resolution of organ dysfunction (organ resolution is defined as having a total SOFA score of ≤ 1) at Day 14

- Resolution of specific organ dysfunction defined as having an individual organ SOFA score of ≤ 1 at Day 14
- Critical care and hospital stay parameters
 - Hospital length of stay
 - ICU length of stay
 - ICU-free days in 28 days
 - Ventilator days
 - Ventilator free days in 28 days
 - Vasopressor days
 - Vasopressor free days in 28 days
 - RRT free days (days alive and free of RRT) in 28 days
- Patient survival at Days 14 and 28
- Presence of Stages 1, 2 or 3 AKI (using the KDIGO criteria) in patients with abdominal sepsis or NSTI

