4.2 Secondary Effectiveness Endpoints

The secondary effectiveness endpoints for this study are:

- Freedom from durable loss of renal function at Day 14
- Freedom from durable loss of renal function at Day 90

Reference creatinine values, baseline AKI stage and percentage loss of eGFR at Days 14 and 90 will be determined through algorithmic determination (see details above). Percentage loss of eGFR determined algorithmically will be based on a comparison of eGFR at screening compared to an algorithmically determined reference creatinine value

- Resolution of organ dysfunction (organ resolution is defined as having a total mSOFA score of ≤ 1) at Day 14
- Resolution of specific organ dysfunction (defined as having an individual organ mSOFA score of ≤ 1) at Day 14
- Critical care and hospital stay parameters
 - Hospital length of stay
 - ICU length of stay
 - ICU-free days in 28 days
 - Days on ventilator
 - Ventilator free days in 28 days
 - Vasopressor days
 - Vasopressor free days in 28 days
 - Discharge status

- Patient survival at Days 14, 28 and 90.
- Presentation of Stages 1, 2, or 3 AKI (using the KDIGO criteria)
- **Stratifications involving Day 14 mSOFA \leq 1 vs Day 14 mSOFA \geq 2**
 - Compare critical care between Day 14 mSOFA \leq 1 vs Day 14 mSOFA \geq 2
 - Compare dose groups in those with Day 14 mSOFA \leq 1
 - Compare dose groups in those with Day 14 mSOFA \geq 2
- Among patients presenting with cardiovascular failure (shock), dose group predicting Day 14 mSOFA \leq 1
- Survival to Day 90 as a function of *freedom from durable loss of renal function at 28* (overall and by dose group)

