5.3 Secondary Endpoints

The same analysis as described above will be performed for freedom from durable loss of renal function at Days 14 and 90 and from improvement for freedom from durable loss of renal function as Days 14, 28, and 90.

Additional secondary endpoints include mSOFA over time, critical care and hospital stay parameters (ICU and ICU-free days, ventilator days and –free days, vasopressor days and –free days, and hospital length of stay (LOS)). Analyses for these endpoints will generally be descriptive, with emphasis on characterizing clinical effect sizes. Nominal p-values will be presented. Categorical outcomes will be described using counts and percentages with nominal p-values determined through chi-square or exact methods. Critical care and hospital stay endpoints will be described using non-parametric approaches including using concordance statistics to characterize clinical effect sizes and Wilcoxon rank sum tests to determine nominal statistical significance. Methods appropriate for time-to-event endpoints including survival and life-table methods will be used for time-to-recovery endpoints.

5.4 mSOFA

The Sequential Organ Failure Assessment score or SOFA was originally developed to track a patient's status during a stay in an intensive care unit (ICU)^{4,5}. Each of six organ systems are evaluated and assigned ordinal scores from 0 to 4. A total score is the sum of the component scores. For this study, the liver component is excluded from the sum score and the resulting sum score is referred to in this study as 'mSOFA'.

Several approaches will be taken to summarize changes over time and between treatment groups in the clinical scores as described below. Special handling of mSOFA scores includes the following:

1. If an individual organ score is missing but other scores for that day are non-missing, the organ systems that were not evaluated are assumed to be free of organ failure and given a value of zero when determining the sum score.
2. If all organ scores are missing for a specific day, the mSOFA total score from that day will be imputed using LOCF with the following exception, LOCF will not be performed after patient death.
3. When summarizing the individual organ scores apart from the mSOFA total scores, the same rules as above will apply.

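### The SAP replaces the protocol's six-organ Day 14 resolution endpoint with a five-organ score that omits the liver, gives no reason, and plans no six-organ rate

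*SAP*

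**What the plan says.** Protocol 6.1 requires a SOFA of at least 2 at entry, "in any one or combination of the 6 major components of the SOFA score". Protocol 9.2.10.1 describes the follow-up score as "Measurements of 6 organ systems, including CNS. To be measured on Days 1, 3, 7, and 14, and calculated retrospectively". Protocol 10.2 then sets the secondary endpoint: "organ resolution is defined as having a total SOFA score of" 1 or less, at Day 14. Section 12.2 repeats it. Neither section leaves out an organ.

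SAP 3.7.1 lists the same six organ systems and then states: "For this study, the liver component is excluded in the primary total sum score". It names the result mSOFA. SAP 5.4 repeats that "the liver component is excluded from the sum score". SAP 4.2 carries this into the endpoint: "Resolution of organ dysfunction (organ resolution is defined as having a total mSOFA score of" 1 or less, at Day 14. SAP 8.4 assigns that analysis to Table 14.2.4.5.

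SAP section 1 says that the SAP prevails where the two documents differ, so mSOFA is the operative definition. The SAP gives no rationale and does not identify the change as a departure from the protocol.

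**The concern.** The endpoint keeps its name but measures something else. Patients enter on a six-organ score and are judged resolved on five, in a trial of abdominal and soft-tissue sepsis where the protocol itself counts the liver among the organs to be scored. A patient with raised bilirubin at Day 14 can be reported as having resolved organ dysfunction, and the rate that the protocol promised is never computed.

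The same cut-off is reused. It defines the Day 14 mSOFA stratifications and the shock analysis in SAP 4.2, a subgroup in SAP 5.6 and 8.8, Tables 14.2.4.5 to 14.2.4.8, Table 14.2.5.5, and two of the Day 90 mortality life tables in Appendix 1.

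**Working it through.** **Inputs.** The SOFA table in Protocol Appendix C and SAP 15.3 has six organs, each scored 0 to 4. The bilirubin row gives 0 below 1.2 mg/dL, 1 for 1.2–1.9, 2 for 2.0–5.9, 3 for 6.0–11.9 and 4 for 12.0 or more. The cut-off for resolution is 1 or less in both documents.

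**The plan's own figure.** SAP 15.3 gives a range of 0–24. Six organs × 4 points = 24, so the printed range is the six-organ score. The mSOFA maximum is 5 × 4 = 20.

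**Which score patterns count as resolved.**

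- Six organs, total 1 or less: all zeros (1 pattern) or a single organ at 1 (6 patterns) = 7.
- mSOFA 1 or less: the five non-liver organs are all zero (1) or one of them is at 1 (5), so 6 patterns. The liver may take any of its 5 values: 6 × 5 = 30.
- Difference: 30 − 7 = 23.

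**What the 23 contain.**

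| Other five organs | Liver score | Patterns |
|---|---|---|
| All 0 | 2, 3 or 4 | 3 |
| One organ at 1 | 1 | 5 |
| One organ at 1 | 2, 3 or 4 | 5 × 3 = 15 |

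Eighteen (3 + 15) have a liver score of 2 or more. Twelve (2 + 5 × 2) have a liver score of 3 or 4, that is, bilirubin of at least 6.0 mg/dL. The largest six-organ total still called resolved is 1 + 4 = 5. No pattern is resolved on six organs but unresolved on mSOFA, because removing a non-negative item cannot raise the sum. These are counts of patterns, not of patients.

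**One record.** Bilirubin 12 mg/dL with all other organs at 0 gives mSOFA 0 (resolved) and SOFA 4 (not resolved).

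**Entry.** Take an illustrative patient with reference creatinine 0.7 mg/dL, screening creatinine 1.5 mg/dL, bilirubin 1.5 mg/dL and no other points. The ratio 1.5/0.7 = 2.1 is Stage 2 AKI. Renal score 1 plus liver score 1 gives SOFA 2, which satisfies the entry score. mSOFA is 1, so the resolution threshold is met before dosing.

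**Are the data available?** SAP 3.8 schedules bilirubin at Screening and on Days 1, 3, 7 and 14. For the Day 14 visit, Protocol 7.3 adds: "Platelet count, creatinine and total bilirubin values required for SOFA components can be obtained from safety laboratories performed at this visit". Scheduling does not explain the omission.

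**The case against.** The strongest reply is that mSOFA is an openly declared choice. The SAP names it, defines it twice, labels the endpoint accordingly and is to be finalized before unblinding. The endpoint is secondary, mainly descriptive, and carries nominal p-values. Six-organ SOFA totals appear in the Appendix 1 titles of Tables 14.2.4.1, 14.2.4.3 and 14.2.4.4. All of this stands and limits the weight of the point. It does not supply the protocol's rate: those tables give scores and changes over time, not the proportion at 1 or less.

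Several stronger readings are tempting but not supported:

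- *A reader might infer that any patient left with liver failure is called resolved.* That happens only if the other five organs sum to 0 or 1.
- *A reader might infer that liver harm would be invisible.* It could not show in the total-resolution row, but SAP 9.2.1 plans chemistry shift and critical-value tables, and 9.2.2 plans a hepatic safety table.
- *A reader might infer that the organ-specific rows leave out the liver.* The text is ambiguous. SAP 8.4 refers to individual organ SOFA scores, SAP 4.2 to individual organ mSOFA scores, and SAP 5.4 to five organ components.
- *A reader might infer that many patients qualify on the liver alone.* All patients need Stage 2 or 3 AKI, and a renal score of 0 needs creatinine below 1.2 mg/dL. Stage 2 by creatinine ratio would then need a reference below 1.2/2 = 0.6 mg/dL. The liver-only case is therefore largely confined to such low references or to entry by urine output or RRT with near-normal creatinine. The renal-plus-liver case above is less restricted.

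The remedy is also not complete. Both documents score an unmeasured component as normal, so a missing bilirubin would still count as 0 on six organs.

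**Conclusion.** The mismatch is established from the text. The SAP's Day 14 resolution endpoint is not the protocol's, no reason is given, and the protocol's version is not planned anywhere. The direction is certain: on the same records, the mSOFA rate is equal to or higher than the six-organ rate.

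The size is unknown. A reader might multiply an assumed resolution rate by an assumed share of patients with residual liver points, but the documents give neither figure. A calculation limited to liver scores of 2 or more would also miss the five patterns with liver 1 plus one other point. Nor do the documents show any effect on the difference between arms, since the same rule applies to both.

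The consequence is confined to this secondary endpoint and the analyses that reuse its cut-off. The primary endpoint, alpha, power and sample size do not depend on it. The change is worth making because it is cheap and decides what this endpoint can be said to show.

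**What to change.** In SAP 4.2, 5.4, 8.4 and Table 14.2.4.5:

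- Report the proportion with six-organ SOFA of 1 or less at Day 14, by arm, as the protocol-defined endpoint.
- Show the mSOFA proportion beside it, labelled as a modified version.
- State before unblinding why the liver is dropped from mSOFA.
- Make clear that the organ-specific resolution rows include the liver, and use one wording for them throughout.

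The cost is SAP wording and one more table row. The necessary bilirubin values are already scheduled. The downside for the sponsor is that the six-organ resolution rate may be somewhat lower.
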